### **3.3.6 Overall survival (OS)**

Overall survival is defined as the time from the date of randomization until death due to any cause regardless of whether the patient withdraws from randomized therapy or receives another anti-cancer therapy (i.e. date of death or censoring – date of randomization + 1). Any patient not known to have died at the time of analysis will be censored based on the last recorded date on which the patient was known to be alive (SUR\_DAT, recorded within the SURVIVE module of the eCRF). For any patients who have not known to have died and are ongoing treatment or do not have a completed survival follow-up eCRF, at the time of OS analysis the last known alive date for each individual patient is defined as the latest among the following dates recorded on the eCRFs:

- AE start and stop dates
- Admission and discharge dates of hospitalization
- Study treatment date
- End of treatment date
- Laboratory sample dates
- Date of vital signs

- Date of ECGs
- Concomitant medications start and stop dates
- Disease assessment dates on IWCLL 2018 eCRF
- Start and stop dates of alternative anti-cancer treatment
- Date last known alive on survival status eCRF
- End of study date.

At the time of the planned final analysis, a survival sweep may be conducted. All subjects who are on study and not known to have died before the survival sweep may be contacted at that time.

If a patient is known to have died where only a partial death date is available then the date of death will be imputed as the latest of the last date known to be alive +1 from the database and the death date using the available information provided:

- a. For Missing day only – using the 1st of the month
- b. For Missing day and Month – using the 1st of January

If death has been recorded but the date is entirely missing, then date of death will be imputed as the date the patient was last known to be alive + 1.

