7.2 Lost to follow-up

A subject will be considered potentially lost to follow-up if he or she fails to return for scheduled visits and is unable to be contacted by the study site.

The following actions must be taken if a subject fails to return to the clinic for a required study visit:

- The site must attempt to contact the subject and reschedule the missed visit as soon as possible and counsel the subject on the importance of maintaining the assigned visit schedule.
- Before a subject is deemed lost to follow-up, the investigator or designee must make every effort to regain contact with the subject or through their family, or by contact with subject's current physician, e.g., by repeat telephone calls, certified letter to the subject's last known mailing address, or local equivalent methods. If a public death registry is available, death information (i.e., date of death) should be collected where allowed by regulatory and EC requirements.
- All attempts to contact the subject should be made routinely and recorded in eCRF on the survival status module. The site should report the attempted date of contact and the last date known to be alive.
- If contact or registry/public source is unsuccessful (or no clear status can be obtained), list subject's status as "unknown" and continue the contact attempts until end of the study (until final analysis).
- Patients should not be marked as lost to follow-up on the Termination (DS) module until the end of the study (at final analysis) when all attempts to collect survival follow-up have been exhausted.
- At the time of final analyses, all enrolled subjects' survival status in the safety analysis set should be re-checked, including those subjects who have withdrawn consent or are classified as "lost to follow-up."
 - Subjects who have withdrawn consent: In the event that the subject has actively withdrawn consent to the processing of their personal data, the survival status of the subject can be obtained by site personnel from publicly available death registries (if available) where it is possible to do so under applicable local laws, to obtain a current survival status in the 7 days following data cut-off. (The applicable CRF modules will be updated.)

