9.4.1.5 Overall survival

Overall survival is the length of time from randomization until the date of death due to any cause. Any patient not known to have died at the time of analysis will be censored based on the last recorded date on which the patient was known to be alive.

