### **3.3.5 Time to next therapy (TTNT)**

TTNT is defined as the time from the date of randomization until institution of non-protocol specified treatment for CLL (either medication or radiotherapy for CLL) or death due to any cause, whichever comes first (i.e. date of first subsequent cancer therapy/death or censoring – date of randomization + 1). Any patient not known to have had a first subsequent anti-cancer therapy will be censored at the last date that the patient was known not to have received a first subsequent anti-cancer therapy (obtained from the CAPRX1 and CAPRXRCL1 forms). If the follow-up cancer therapy eCRF has not been completed then the last known alive date will be used for censoring, considering the following eCRFs:

- AE start and stop dates
- Admission and discharge dates of hospitalization
- Study treatment date
- End of treatment date
- Laboratory sample dates
- Date of vital signs
- Date of ECGs

- Concomitant medications start and stop dates
- Disease assessment dates on IWCLL 2018 eCRF
- Start and stop dates of alternative anti-cancer treatment
- Date last known alive on survival status eCRF
- End of study date.

Patients who are ongoing randomized treatment will be censored at the date of last study visit, using the same criteria defined above. If a patient terminated the study for reason other than death without subsequent therapy, these patients will be censored at the earliest of their last known to be alive and termination dates. For the Interim Analysis, DCO date will be used.

Subsequent anticancer therapies are defined as medications/radiation therapies that:

- Had an indication for the primary malignancy CLL,
- Had start date after study treatment completion or discontinuation.

The start date of subsequent anticancer therapy is defined as the first dose date of the subsequent anticancer therapy.

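### The fallback censoring rules for OS and TTNT accept an end-of-study date as proof of life without requiring contact, and the TTNT sentence on the data cut-off is ambiguous

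*SAP*

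**What the plan says.** **OS.** Protocol 9.4.1.5 and SAP 3.3.6 share one default: patients not known to have died are "censored based on the last recorded date on which the patient was known to be alive". The SAP takes that date from the SURVIVE module. It adds a fallback for patients who "are ongoing treatment or do not have a completed survival follow-up eCRF": "the last known alive date for each individual patient is defined as the latest among the following dates recorded on the eCRFs". Most items on the list record something that happened to the patient, such as a visit, sample, dose or event. The last item is "End of study date".

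**TTNT.** In SAP 3.3.5 the default is the last date the patient was known not to have started subsequent therapy. The fallback is: "If the follow-up cancer therapy eCRF has not been completed then the last known alive date will be used for censoring". The list that follows is the same and again includes the end-of-study date. For patients who left the study alive without subsequent therapy, "these patients will be censored at the earliest of their last known to be alive and termination dates". The next sentence is: "For the Interim Analysis, DCO date will be used".

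**When the date is entered.** Protocol 7.2 delays the termination entry for lost patients ("Patients should not be marked as lost to follow-up on the Termination (DS) module until the end of the study (at final analysis"). The same section asks sites to record the last date known alive on the survival status module and to re-check vital status at the final analysis.

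**Which analysis was done.** The protocol synopsis states that the cut of 03Jan2024, planned as the interim, was treated as the final analysis.

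**The concern.** Censoring is sound only up to the last day on which the patient's status was actually known. An end-of-study entry may be made with no contact at all. Under a latest-of rule, one such entry replaces every genuine contact before it. Protocol 7.2 makes that entry late by design for lost patients, however early contact ended. The patient is then counted as alive, or alive and untreated, over time that nobody observed. That departs from protocol 9.4.1.5.

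For TTNT there are two further problems. The earlier-of rule looks like a safeguard, but it compares the termination date with a last-alive date that may be that same date. The DCO sentence follows directly on the rule for patients who left the study and is not restricted to those still in follow-up. The SAP does not say whom it covers, or whether it still applies once the interim is treated as final.

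At stake are two secondary endpoints with formal log-rank tests (SAP Table 7) in an open-label trial. Overstated event-free time would affect the Kaplan-Meier estimates and the reported follow-up. Unequal loss between arms would also affect the hazard ratio.

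**Working it through.** The documents give no figure for the effect of these rules, so there is none to reproduce.

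**1. The rules applied to one patient.** Assume randomisation at month 15, last contact at month 27 and a termination entry at month 45. Observed time is 27 − 15 = 12 months. Time to the administrative date is 45 − 15 = 30 months.

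- OS with a completed survival form: 12 months, which is correct.
- OS by the fallback: max(12, 30) = 30 months, of which 18 are unobserved.
- TTNT, earlier-of rule with last-alive taken from the list: min(30, 30) = 30 months. It gives 12 only if last-alive comes from real contacts.
- TTNT, DCO sentence read literally, DCO at month 45: 30 months.
- TTNT, DCO read as standing in for the termination date, last-alive from real contacts: min(12, 30) = 12 months, which is correct.

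**2. Size in patient-time, worst case (every dropout reaches the administrative date).** Inputs are 150 patients and 30 months' accrual (Protocol 9.2), and analysis at about month 45 (Protocol 4.4). Uniform accrual is assumed and deaths and events are ignored. Follow-up then runs from 15 to 45 months with mean 30, so the total is 150 × 30 = 4,500 patient-months.

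- Protocol 9.2, about 5% dropout by the final analysis, spread evenly over follow-up (assumption): 7.5 patients × 15 months = 112.5, and 112.5/4,500 = **2.5%**.
- SAP 1.3, 5% by 14 months, all within the first 14 months and evenly spread (assumption): mean gap 30 − 7 = 23 months; 7.5 × 23 = 172.5, and 172.5/4,500 = **3.8%**.
- SAP 1.3, the same 5% by 14 months as a constant rate that continues (assumption): rate = −ln(0.95)/14 = 0.00366 per month. The mean proportion lost by month 45 is 1 − (e^(−15 × rate) − e^(−45 × rate))/(30 × rate) = 10.4%. The unobserved time per randomised patient is 30 − 0.1036/0.00366 = 1.71 months; × 150 ≈ 257, and 257/4,500 = **5.7%**.

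**3. Effect on the hazard ratio.** This was simulated with exponential times, 30 months' uniform accrual and a cut at month 45, again with every lost patient carried to the cut. The hazard ratio is the ratio of events per patient-time, Arm A over Arm B. Event rates and loss by arm are assumptions: 36-month OS of 85% or 93% with HR 1.00; TTNT 50% event-free at 36 months in Arm B with HR 0.35. Each lost patient gains about 17 to 18 months.

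| Assumed loss, A / B | Added patient-time, A / B | OS HR (85% case): last contact → administrative date | TTNT HR: last contact → administrative date |
|---|---|---|---|
| 5% / 5% | 2.9% / 2.9% | 0.994 → 0.993 | 0.349 → 0.349 |
| 2% / 10% | 1.1% / 5.9% | 1.007 → 1.055 | 0.350 → 0.368 |
| 10% / 2% | 5.9% / 1.1% | 1.000 → 0.954 | 0.349 → 0.333 |
| 5% / 15% | 2.9% / 9.2% | 0.996 → 1.057 | 0.350 → 0.374 |

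Added patient-time is from the OS runs. The shift is the ratio of the two inflations: 1.059/1.011 = 1.05 in the second row and 1.092/1.029 = 1.06 in the fourth. Equal loss leaves the hazard ratio unchanged. Unequal loss of this order moves it about 5 to 7% in favour of the arm that loses more.

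**The case against.** The strongest reply is that the plan already protects most patients, and that the mechanism should rarely have operated at the cut that was analysed.

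- **The OS rule at issue is only a fallback.** Protocol 7.2 asks sites to report the last date known alive and to update the SURVIVE module for lost patients. A patient handled that way is censored correctly for OS. Those still on treatment have no end-of-study date. This stands.
- **Timing.** If lost patients are not marked as lost until the final analysis, few should have carried such an entry on 03Jan2024. SAP 4.2.3 excludes data entered after the DCO, apart from survival-sweep forms. Patients terminated earlier would mainly be withdrawals, for whom the date may be a real contact. This stands, so one cannot say that the latest-of rule always selects an administrative date.
- **The DCO sentence has a harmless reading.** Lost patients have no termination date at an interim, so the DCO may simply replace it in the earlier-of rule. That is possible, but the SAP does not say so, and the reading protects only if last-alive comes from real contacts.
- **Consequence.** Alpha is allocated to PFS alone (SAP 4.2.1), and PFS is censored at the last adequate disease assessment. This stands.

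A reader might infer that OS, too, is censored at the DCO for everyone. The documents do not support that. The DCO sentence is in the TTNT section only. For OS, SAP 4.2.3 uses the DCO for patients whose later status is known from the survival sweep, which is correct practice.

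**Conclusion.** The point holds as a defect in two written derivations. The fallback lists treat an end-of-study date as evidence of being alive without requiring contact, the TTNT earlier-of rule does not repair this, and the TTNT DCO sentence can be read in two ways that give different censoring dates. That sentence matters because the analysis performed was the planned interim.

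The size is probably small. The figures of 2.5% of patient-time (protocol dropout) and about 4 to 6% (SAP dropout) are worst cases: they assume that every dropout is carried to the administrative date, and they depend on the assumed dropout pattern. Completed survival forms, in-person withdrawals and the timing rules all reduce them.

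It is tempting to conclude that the reported OS and TTNT are inflated by these amounts, or that the treatment comparison is biased. The documents support neither. They do not show how many patients reach the fallback, and both state equal dropout in the two arms, under which the hazard ratio is essentially unchanged. A shift of 5 to 7% needs an imbalance that is assumed here and not documented. The sizing and result of the primary PFS analysis are not touched.

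**What to change.** In SAP 3.3.5 and 3.3.6:

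1. Accept the end-of-study date only when the termination record documents contact, or known vital status, on that day.
2. Define last known alive from actual contacts, and use that definition in both sections.
3. For TTNT, censor at the last date on which therapy status was ascertained. Knowing that a patient is alive does not show that no therapy has started.
4. Replace the DCO sentence with an upper cap: censor at min(last date documented alive and therapy-free, DCO). Say that it applies at every analysis. For OS the same cap applies to the last date documented alive.

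If outputs already exist, re-derive the two endpoints and report how many patients change, by arm. The cost is SAP wording and one derivation. The downside is slightly shorter reported follow-up.

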### 3.3.7 Minimal residual disease (MRD) negative rate

If the patient's physical examination findings, laboratory evaluations, and radiographic evaluations suggest that PR, CRi, or CR has been achieved, a peripheral blood and bone marrow sample will be assessed between 8-12 weeks from the time of supportive clinical assessments to determine MRD negativity. MRD negative rate (peripheral blood) at the start of Cycle 9 will be tested. MRD negative is defined as < 1 CLL cell per 10,000 leukocytes. MRD negative rate is defined as the proportion of subjects with MRD-negativity.

## 3.4

CCI

### 3.4.1

CCI

CCI

CCI

CCI

### 3.5 Safety Variables

#### 3.5.1 Exposure and dose interruptions

Exposure (i.e. duration of treatment) will be calculated as follows for acalabrutinib, rituximab and chlorambucil:

Total (or intended) exposure of study drug for acalabrutinib:

- Total (or intended) exposure =  $\min(\text{last dose date where dose} > 0 \text{ [units]}, \text{date of death, date of DCO}) - \text{first dose date} + 1$

Total (or intended) exposure of study drug for rituximab:

- Total (or intended) exposure =  $\min(\text{last dose date where dose} > 0 \text{ [units]} + 27, \text{date of death, date of DCO}) - \text{first dose date} + 1$

Total (or intended) exposure of study drug for chlorambucil:

- Total (or intended) exposure =  $\min(\text{last dose date where dose} > 0 \text{ [units]} + 13, \text{date of death, date of DCO}) - \text{first dose date} + 1$

Actual exposure of study drug:

- Actual exposure = intended exposure – any length of time where the patient has not taken any of the planned dose. For rituximab, actual exposure will be calculated as Total exposure - sum of positive values of (date of subsequent dose – [date of previous dose + 28]). For chlorambucil, actual exposure will be calculated as Total exposure - sum of positive values of (date of subsequent dose – (date of previous dose + 14)).

The actual exposure calculation makes no adjustment for any dose reductions that may have occurred.

### Missed or forgotten doses

For acalabrutinib missed and forgotten doses should be recorded on the EX eCRF page as a dose interruption with the reason recorded as “Subject forgot to take dose”. These missed or forgotten doses will not be included as dose interruptions in the summary tables but the information will appear in the listing for dosing. However, these missed and forgotten doses will be considered in the derivation of actual exposure.

### Patients who permanently discontinue during a dose interruption

If a patient permanently discontinues study drug during a dose interruption, then the date of last administration of study medication recorded on the DOSDISC eCRF page will be used in the programming.

### Dose intensity

Relative dose intensity (RDI) is the percentage of the actual dose delivered relative to the intended dose through to treatment discontinuation. CCI [REDACTED]

- [REDACTED]
- [REDACTED]
- [REDACTED]

### 3.5.2 Adverse events

AEs will be collected throughout the study, from date of informed consent until 30 days after the last dose of study drug. SAEs will be collected from the date of informed consent. The following events will be considered treatment emergent:

- Adverse events with an onset date on or after first dose of study drug, and within 30 days after last dose of study drug or the initiation of a subsequent therapy (including crossover treatment), whichever occurs first.
- Worsening of pre-existing events on or after first dose of study drug, and within 30 days after last dose of study drug or the initiation of a subsequent therapy (including crossover treatment), whichever occurs first.

The Medical Dictionary for Regulatory Activities (MedDRA) (using the latest or current MedDRA version) will be used to code the AEs. AEs will be graded according to the

National Cancer Institute Common Terminology Criteria for AEs (using the NCI CTCAE version 5.0).

### **AEs of special interest**

The following events are adverse events of special interest (AESIs) for subjects randomized to the acalabrutinib treatment arm and must be reported to the sponsors expeditiously irrespective of regulatory seriousness criteria or causality:

Ventricular arrhythmias (e.g., ventricular extrasystoles, ventricular tachycardia, ventricular arrhythmia, ventricular fibrillation, etc.) as defined in [Appendix A](#).

### **Adverse Events of Clinical Interest**

Some clinical concepts (including some selected individual preferred terms and higher-level terms) have been considered “Events of Clinical Interest” (ECI) to the acalabrutinib program. ECI include cardiac events, cytopenias (anemia, leukopenia and thrombocytopenia), hemorrhage, hepatotoxicity, hypertension, infection, intestinal lung disease/pneumonitis, tumor lysis syndrome, and secondary primary malignancy.

These ECIs have been identified as a list of categories provided by the patient safety team. ECIs are defined in [Appendix A](#).

Other categories may be added as necessary or existing terms may be merged. An AstraZeneca medically qualified expert after consultation with the Global Patient Safety Physician has reviewed the events of clinical interest and identified which higher-level terms and which preferred terms contribute to each ECI. Further reviews may take place prior to database lock (DBL) to ensure any further terms not already included are captured within the categories.

### **3.5.3 Clinical laboratory data**

Clinical safety laboratory assessment is included in Table 6 and specified into the CSP SoA for the timing and frequency.

**Table 6 Laboratory Variables**

Clinical Chemistry a	
Calcium	Urea or blood urea nitrogen
Chloride	Uric acid
Magnesium	Creatinine
Phosphate/Phosphorus	Total bilirubin
Potassium	Glucose
Sodium	Albumin

**Table 6 Laboratory Variables**

AST	Total protein
ALT	Triglycerides
Alkaline phosphatase (ALP)	Cholesterol
Gamma glutamyl transferase (GGT)	Lactate dehydrogenase (LDH)
Hematologyb	
White blood cell (WBC) count with differential	Platelet count
Red blood cell (RBC) count	Absolute neutrophil count (ANC)
Hematocrit	Absolute lymphocyte count (ALC)
Hemoglobin	
Pregnancy Test (females of childbearing potential only)	
Urine human chorionic gonadotropin (hCG) or Serum $\beta$ hCG	
Hepatitis B and C Testingc	
HBsAg	Hepatitis B surface antibody (HBsAb)
Anti-HBc	Hepatitis C (hepatitis C virus [HCV]) antibody
Hepatitis B PCR (clinically indicated)	Hepatitis C PCR (clinically indicated)
Other Tests	
T/B/NK Cell Count	Serum immunoglobulin levels
$\beta$ 2-microglobulin b	
Cytogenetics and FISH Panel b,d	Genetic molecular prognostic molecules b,e

a In case a patient shows an AST or ALT  $\geq 3 \times$ ULN together with total bilirubin  $\geq 2 \times$ ULN please refer to CSP Appendix D 'Actions required in cases of increases in liver biochemistry and evaluation of Hy's Law,' for further instructions.

b These tests will be performed at the central laboratory.

c Hepatitis serology testing must include HBsAg, HBsAb, anti-HBc and hepatitis C (HCV) antibody. In addition, any patients testing positive for anti-HBc must have quantitative PCR testing for HBV DNA during screening and monthly thereafter. Monthly monitoring should continue until 12 months after last dose of study drug(s). Any patient with a rising viral load (above lower limit of detection) should discontinue study drug and have antiviral therapy instituted and a consultation with a physician with expertise in managing hepatitis B. Since IVIG may cause false positive hepatitis serology, monthly PCR testing is not required in patients who are currently receiving or received prophylactic IVIG within 3 months before study enrollment and have a documented negative anti-HBc test before the initiation of IVIG therapy. PCR testing should be performed when clinically indicated (eg, in the setting of rising transaminase levels). Patients with a known history of hepatitis C or who are hepatitis C-antibody positive should have quantitative PCR testing for HCV RNA performed during screening. No further testing is necessary if the PCR results are negative at screening.

d Cytogenetics and FISH Panel include 17p del, 13q del, trisomy 12, 11q del by FISH and stimulated karyotyping.

e Genetic molecular prognostic molecules panel include, but is not limited to, sequencing of p53 mutations, immunoglobulin heavy-chain variable (IGHV) mutational status.

